
approval to gather data on neighborhood adversity for all treatment groups through Geolytics.

Our specific aims are:

Aim 1: Estimate NV-C differences in markers of chronic disease and mortality. The NV group is hypothesized to have: *H1: lower measures of obesity; H2: lower risks for macrovascular disease reflected in measures of functional arterial stiffness; H3: fewer markers of chronic kidney disease (CKD); H4: better metabolic outcomes; H5: lower levels of immune/inflammatory markers; and H6: lower mortality rates.*

Aim 2: Examine modifiers of the intervention on outcomes in H1-5. *H7: Given results through age 18, NV effects on H1-5 outcomes will be greater for mothers of females and female offspring.*

Aim 3: Explore mediators of NV on selected outcomes: *H8: NV effects on maternal outcomes will be mediated, in part, by earlier NV beneficial effects on prenatal health behaviors, PIH, preterm delivery in first and subsequent births, closely spaced subsequent pregnancies, maternal sense of mastery, stable family structure, family economic resources, and hypertension at 12 and 18 years postpartum. H9: NV effects on offspring outcomes will be mediated, in part, by NV beneficial effects on prenatal health behaviors, PIH, preterm delivery, breastfeeding, qualities of parental care, lower screen-time, stable family structure, family economic resources, and obesity at ages 12 and 18.*

Background

Significance

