Measured Maternal Obesity, Hypertension, and Self-Reported Health Problems. By the first offspring's 18th birthday, nurse-visited (T4) women were less likely to have stage-1 hypertension (at the year 12 and 18 assessments) than women in the control group (T2), effects limited to mothers of females.⁷² In addition, nurse-visited (T4) women reported fewer thyroid problems, kidney problems, and among mothers of females, fewer memory problems.⁷² The presence of hypothyroidism among women with chronic kidney disease increases the risk for serious heart disease.⁷⁷ The one exception to this pattern is that nurse-visited women reported more problems with high cholesterol, an effect essentially limited to those who gave birth to males (not shown).⁷²

Hypothesized Pathways of Program Effects on Maternal Chronic Disease

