H2: Risks for Macrovascular Disease. We will compare NV and C participants on measures of arterial stiffness: peripheral systolic and diastolic BP (averaged over the two assessments), cfPWV, and AI.

H3: Markers of Chronic Kidney Disease (CKD). We will compare NV and C participants on the estimated Glomerular Filtration Rate (eGFR) and the microalbumin/creatinine ratio.

H4: Metabolic Outcomes: We will compare NV and C participants on measures of Glycosylated Hemoglobin (HbA1C), dyslipidemia (TC, LDL, HDL, TG), and the AST/ALT ratio.

H5: Immune/Inflammatory Markers: We will compare NV and C participants on immune/inflammatory markers [hsCRP, fibrinogen, interleukin 6 (IL-6), tumor necrosis factor alpha-receptor 2 (TNF-2), and insulin-like growth factor-1 (IGF-1 – free and total)].

H6: Mortality. We will compare NV and C participants on rates, ages, and causes of death.

The interpretation of outcomes specified in H1-6 will take into consideration the presence of existing disease and disabilities, based upon interviews, records of medication, diagnoses, and hospitalization records.

Approach to Specific Aim Two (Examine Moderators of Intervention Effects)

As elaborated below, we will examine all outcomes in this study in statistical models that employ sex of offspring as a classification factor and maternal psychological resources cross-classified with Treatment condition (NV-C). We have hypothesized (H7) that intervention effects (H1-5) will be more pronounced among females and mothers who gave birth to females, so analyses of NV-C differences will focus on these groups. We have elaborated methods to address this aim under the statistical methods and models below.

Approach to Specific Aim Three (Explore Mediators of NV Effects)

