The primary analyses will make use of general linear model methods and their extensions.⁸⁹⁻⁹⁴ The focus will be on (1) full model specification to account for all sources of variation, and full examination of interactions among model factors, including examination of homogeneity of regressions to understand interactions between classification effects and covariates; (2) generalized models to analyze dichotomous outcomes with binomial error distributions and count data assumed to have negative binomial distributions; (3) generalized linear mixed models (including repeated measures and growth-curve models) to account for correlated data and to examine differences in change over time; (4) semiparametric methods to model relations between variables without requiring a specific functional form;⁹⁵ (5) survival analyses including Kaplan-Meier, competing risks and Cox hazard models;⁹⁶⁻⁹⁹ (6) mediation analyses using structural equation models to examine causal processes, including the direct and indirect effects of treatment on outcomes.^{100,101}

The primary classification factors for examination in our models, as determined by our hypotheses and earlier work, include treatments (Control vs. Nurse Visited - T), maternal psychological resources (low versus high based on a median split – P), sex of offspring (S), and follow-up time (A) for outcomes assessed at multiple time points (e.g. obesity) – T|P|S and T|P|S|A. Covariates will be selected using a post-double-selection lasso (least absolute shrinkage and selection operator) procedure.¹⁰²⁻¹⁰⁴ This procedure will select covariates that are most related to intervention status (i.e. differences at randomization) or related to the dependent variable. Candidate covariates will include an index of household poverty, obesity, and maternal

pre-pregnancy BMI.

Statistical Power/Smallest Detectable Differences for Proposed Follow-Up

Given that sample size is fixed, we show below calculations of the smallest detectable treatment-control differences for the 29-year follow-up. Calculations for representative outcomes were carried out with the following assumptions: a Type I error of .05, Type II error of .20 (power of .80), 2-tailed tests, 10 percent of the variance accounted for by other terms in the model for normally distributed variables and N=600. Disproportionate sample sizes in Control and Nurse-Visited groups are taken into account.

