Smallest Detectable Program Effects. Table 6 displays the smallest detectable treatment differences. The study has sufficient power to detect small to moderate effect sizes for normally distributed variables for tests of treatment main effects (.24 SD) and moderate effect sizes (.33 SD) for tests conditioned by a single factor that is evenly distributed between two levels (e.g., offspring sex). For outcomes that are dichotomous, our calculations of smallest detectable treatment differences are calculated in the binomial logistic-linear model and shown for a range of base rates likely to be found in our outcomes. It is important to note that we have detected program effects of this magnitude in earlier phases of the trial and that we have seen that some intervention effects are larger as the mothers and offspring age. We will not make adjustments for multiple comparisons of the primary outcomes (Hypotheses 1-5), but will interpret findings with a critical eye concerning chance effects.

Table 7. Smallest detectable treatment effects for treatment main effects and for subgroups defined by sex

Base Rate for OR	Smallest Detectable Treatment Contrasts for ORs		Smallest Detectable Treatment Contrasts for ORs
	Whole Sample N=600	One Half of Sample (e.g., Mothers of Females) N=300	
10%	.33	.14	
20%	.49	.33	
30%	.55	.42	
40%	.59	.46	
	Smallest Detectable Treatment Contrasts for ESs		Smallest Detectable Treatment Contrasts for ESs
	.24	.33	

Note OR = T_4 odds/ T_2 odds; ES = $(T_4 \text{ mean} - T_2 \text{ mean})/\text{pooled standard deviation}$

Tests of Hypotheses

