Hypotheses 1-6 (primary): The NV group is hypothesized to have: H1: lower measures of obesity, (BMI, waist to hip ratios, segmental and % body fat, visceral fat); H2: lower risks for macrovascular disease, reflected in measures of functional arterial stiffness (peripheral BP, cfPWV, AI); H3: fewer markers of CKD - higher eGFR and lower microalbumin/creatinine ratios; H4: better metabolic outcomes (lower levels of HbA1C, TC, HDL, LDLc, TG, AST/ALT ratio); H5: lower levels of immune/inflammatory markers (hsCRP, fibrinogen, IL-6, TNF-alpha receptor 2, IGF-1); and H6: lower mortality rates. We will test Hypotheses 1-5 by examining each of the primary outcomes listed above as dependent variables in our primary T|P|S model, plus covariates from the post-double-selection lasso results. Outcomes also measured at earlier time points will include an additional classification factor for first-born offspring age at assessment (A). We will examine treatment-control difference summing across levels of maternal psychological resources and sex. In addition, we will examine planned contrasts for males and females, and mothers of males and females. Outcomes for hypotheses 1-5 are normally distributed and will be examined in the general linear model or mixed linear model for repeated measure outcomes. Secondary analyses will examine some outcomes in their dichotomous form for those values that cross clinical thresholds (e.g., obesity), which will be analyzed in the logistic model or generalized linear mixed model for repeated measure outcomes.⁹⁰ Hypothesis 6, related to mortality 6, will be examined in survival analysis by treatment condition without additional classification factors consistent with our earlier report on mortality.^{99,69}

Hypotheses 7: NV effects on H1-5 outcomes will be greater for female offspring and mothers who gave birth to females. Planned contrasts in the above aforementioned models for all primary outcomes, with the exception of mortality (given low base rates), will focus on female offspring and mothers of females.

Hypothesis 8: NV effects on maternal outcomes (H1-6) will be mediated, in part, by NV effects on prenatal health behaviors, preterm delivery in first and subsequent births, and PIH in first births; closely spaced subsequent pregnancies, maternal sense of mastery, stable/supportive partnered

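### H7 says effects are larger in females, but the analysis tied to it is within-sex contrasts; the treatment-by-sex contrast already in the model is never named as the H7 test

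*Combined protocol and SAP*

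**What the plan says.** Under the specific aims, Aim 2 states H7 as a comparison of effects: "NV effects on H1-5 outcomes will be greater for mothers of females and female offspring". Tests of Hypotheses repeats it in the same comparative sense.

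The analysis attached to H7 appears in two places:

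- Tests of Hypotheses, Hypothesis 7: planned contrasts from the H1-5 models, mortality excepted, "will focus on female offspring and mothers of females".
- Approach to Specific Aim Two: effects are expected to be more pronounced in females and mothers of females, "so analyses of NV-C differences will focus on these groups". The section then points forward: "We have elaborated methods to address this aim under the statistical methods and models below".

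Three other statements bear on the point:

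- Statistical Models and Methods of Analysis crosses treatment (T), maternal psychological resources (P) and offspring sex (S) as T|P|S, adding assessment time (A) for repeated outcomes. It promises "full examination of interactions among model factors".
- Under Hypotheses 1-6, "we will examine planned contrasts for males and females, and mothers of males and females".
- Smallest Detectable Program Effects gives .24 SD for the treatment main effect and .33 SD for "tests conditioned by a single factor that is evenly distributed between two levels". Table 7 labels the latter column as one half of the sample, N=300.

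**The concern.** An NV-C contrast within females asks whether the effect in females is zero. H7 asks whether that effect exceeds the effect in males. These are different questions. Setting a female result beside a male result does not answer the second one, because one can be significant and the other not when the underlying effects are identical.

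The forward reference from Aim 2 leads to a general statement about interactions and to the female-focused contrasts. It does not lead to a named test of the difference. If H7 were reported from the contrasts tied to it, a common effect of nurse visiting could be described as one that is greater in females. H7 covers all H1-5 outcomes in both generations, so the occasion would arise many times.

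**Working it through.** **Inputs.** From Statistical Power/Smallest Detectable Differences: N=600, two-sided .05, power .80, 10% of variance explained by other model terms. From Smallest Detectable Program Effects: an even sex split, so 300 per stratum. Assumption: the 514:228 allocation of Treatments 2 and 4 carries over to each stratum, giving 207.8 control and 92.2 nurse-visited. Residual variance is taken as common to both sexes. The calculation is for a normally distributed outcome at a single time point.

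**Reproducing the plan's figures.** Smallest detectable difference = (1.960 + 0.842) × SE, with SE = √[(1 − .10)(1/n₂ + 1/n₄)].

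- Whole sample (415.6 and 184.4): SE = .0839; × 2.802 = .235 SD (plan: .24).
- One sex (207.8 and 92.2): SE = .1187; × 2.802 = .333 SD (plan: .33).

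Both agree, so the plan's .33 SD is the sensitivity of an NV-C contrast inside one stratum.

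**Treatment-by-sex contrast.** This is the difference of two independent within-sex contrasts.

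- SE = √2 × .1187 = .1679.
- Smallest detectable difference = 2.802 × .1679 = .470 SD.
- 95% CI half-width = 1.960 × .1679 = .329 SD.
- Power is about 50% at a true female-minus-male difference of .33 SD and about 30% at .24 SD.

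Using the numbers available for the 29-year follow-up gives .470 SD (454:203, mothers) and .469 SD (473:214, offspring). A 45:55 sex split gives .473 SD.

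**What within-sex contrasts do when the sexes do not differ.** Let the true effect be d in both sexes. Then p = P(female contrast significant) = Φ(d/.1187 − 1.96) + Φ(−d/.1187 − 1.96). The strata are independent, so P(female significant, male not) = p(1 − p).

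| Common effect d (SD) | Female significant | Female significant, male not | Treatment-by-sex test rejects |
|---|---|---|---|
| .10 | 13% | 12% | 5% |
| .20 | 39% | 24% | 5% |
| .24 | 52% | 25% | 5% |
| .33 | 79% | 16% | 5% |

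For example, at d = .24, p = .525 and .525 × .475 = .249. The product p(1 − p) cannot exceed 25%, so .24 SD is close to the worst case for that pattern. The 5% is two-sided; in the hypothesized direction it is 2.5%.

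**The case against.** The strongest reply is that the plan already contains what is needed. H7 sits under an aim about effect modification. Sex is a crossed factor in the primary model, the methods section puts interactions among its first-listed priorities, and contrasts for males are planned too. Nothing rules out a female-minus-male contrast. All of this stands: the analysis is available, and what is missing is its designation. It does not close the gap, because the interaction statement covers every factor and covariate, is not tied to H7, and leaves the female-focused contrasts as the only analysis attached to that hypothesis.

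A reader might infer that the plan would count a significant female contrast, or significance in females only, as support for H7. No passage states such a rule. The percentages above show what those patterns are worth as evidence for H7; they are not the error rate of a procedure the plan adopts.

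It can also be said that H1-6 carry no formal success criterion either, and that the plan intends to read results cautiously and for coherence. That is fair, so no special success threshold is asked of H7. Naming the contrast that estimates the hypothesized quantity is a smaller request.

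Finally, Table 7 is not in error. Its title and column label describe subgroups and half the sample, and it claims nothing about an interaction.

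**Conclusion.** The point holds as a mismatch between hypothesis and designated analysis. H7 concerns a difference between effects; the contrasts tied to it estimate effects within a sex and cannot establish that difference. The contrast that can is obtainable from the planned model but is not named for H7.

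In size: with equal effects of .10 to .33 SD in both sexes, the female contrast is significant 13% to 79% of the time, and significance in females only occurs 12% to 25% of the time. The treatment-by-sex test rejects 5% (2.5% in the hypothesized direction). These figures rest on the assumed allocation, an even sex split, common residual variance, and normally distributed single-time-point outcomes. They do not carry over to outcomes analysed with the time factor, because the within-person correlation is not given.

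The documents do not support the stronger inference that effect modification by sex will go unexamined. This is a cheap improvement to the plan.

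**What to change.** Add one or two sentences under Hypothesis 7:

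- H7 is tested by the treatment-by-sex contrast: NV-C in female offspring minus NV-C in male offspring and, for maternal outcomes, NV-C in mothers of females minus NV-C in mothers of males.
- The contrast comes from the planned T|P|S model, or its T|P|S|A counterpart for repeated outcomes, and is reported with a 95% CI.
- The within-sex contrasts are kept as supportive estimates.

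Optionally, note beside Table 7 that its .33 SD applies to a within-sex contrast, and that on the same inputs the smallest detectable treatment-by-sex difference is about .47 SD for normally distributed single-time-point outcomes.

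No new data, model or sample is needed. The cost is a less favourable stated sensitivity for Aim 2.

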At the 29-year follow-up, we expect to complete assessments on approximately 80% of those randomized. **Findings from earlier follow-ups have led to our general hypothesis that, over the life-course, the intervention will lead to reductions in the emergence of cardiovascular disease (CVD), chronic kidney disease (CKD), type 2 diabetes (T2D), and premature mortality among both mothers and their first-born offspring.** We will a) conduct anthropometric assessments; b) draw blood to measure cardio-metabolic and immune-inflammatory factors; c) collect random urines to measure the microalbumin/creatinine ratio; d) evaluate arterial stiffness using SphygmoCor Xcel and a standard BP instrument; and e) classify timing and causes of death from National Death Index (NDI) records. To help with interpretation, we will conduct interviews to assess history of diagnoses, medications, menopause, hospitalizations, disability, sedentary and physical activity, sleep, diet, substance use, depression, anxiety, mastery, duration and quality of partnered relationships, education, work, and incarceration; and review hospitalization records, and state records of government-benefits use. We will estimate Nurse-Visited (NV) - Control (C) differences in these outcome domains for both mothers and first-born offspring. Given that previous follow-ups of the Memphis sample for determinations of maternal and offspring mortality have involved all four of the original treatment conditions in this study, we will assess maternal and offspring mortality in all four of those treatment conditions for this phase of follow-up. Moreover, given that maternal mortality due to natural causes will increase as the mothers age, we plan to follow this sample through 2026. The rates of mortality among offspring also will increase over this age-range, so we will assess offspring mortality over the same years. Earlier phases of this study (protocol 04-0518—now closed) examined neighborhood adversity for treatment groups 1 and 3, which involved sending participants' baseline addresses in these groups at the time of registration in this trial to Geolytics, a firm we used to calculate neighborhood adversity scores. Registration in this trial took place in 1989 and 1990. We now wish to include measures of neighborhood adversity in this study for all four treatment groups. Neighborhood adversity can be treated as a baseline factor that may either moderate treatment effects on mortality or account for variance in our estimates of mortality by treatment condition. We now realize the value in obtaining

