Treatment 3 - Transportation and Nurse-Visitation during Pregnancy Only. The 230 families in this condition received: 1) free transportation for scheduled prenatal care; and 2) intensive nurse home-visitation services during pregnancy and one postpartum visit in the hospital before discharge and one postpartum visit in the home. This group did not receive any other postpartum services or assessments (except death records).

Treatment 4 - Transportation and Nurse-Visitation during Pregnancy and Infancy. The 228 families in this condition received: 1) free transportation for scheduled prenatal care; 2) intensive nurse home-visitation services during pregnancy and through the child's second birthday; and 3) developmental screening and referral services for the child at the 6th, 12th, and 24th months of the child's life.

Note that the trial was structured to follow Treatments 2 and 4 after delivery to minimize study costs, and these two groups have been followed through offspring age 18. In planning the current follow-up, we conducted pilot work and found that our success in tracing T1 and T3 participants would be significantly less

than those in T2 and T4, so we chose not to attempt to follow them.

Program Plan and Implementation

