Number Refused	151				
Number Randomized	1138				
Treatment Group Assignment	1 ^a	2	3 ^a	4	Total (TX 2 & 4)
Number Allocated to Each Treatment	166	514	230	228	742
Not Available for 29-year follow-up					
Miscarriages (first born) not followed	6	19	6	8	27
Stillbirths (first born) not followed	0	5	3	2	7
Offspring deaths before age two (not followed)		7		1	8
Maternal deaths through 18 years postpartum		15		3	18
Post-randomization maternal refusals/drops		14		11	25

Offspring Deaths (after age 2)	9	2	11
Post-randomization offspring refusals/drops	1	1	2
Mothers Available for 29 year follow up	454	203	657
Current mother address in Memphis metro area	380	163	543
Current mother address < 3 hrs. drive Memphis	13	8	21
Current mother address > 3 hrs. drive Memphis	50	29	79
First-Born Offspring Available for 29 year follow FU	473	214	687
Current study child address in Memphis metro area	378	178	556
Current study child address < 3 hrs. drive Memphis	16	6	22
Current study child address > 3 hrs. drive Memphis	79	30	109

^a Sample not followed after birth by design

Summary of NFP Effects from Pregnancy through Child Age 18 on Maternal Outcomes in Memphis Trial

Table 3 summarizes key Control-NV effects found for mothers over the 18-year period following registration in the program during pregnancy. We summarize offspring effects below.

Prenatal/Newborn Health. Nurse-visited women (T3+T4) had fewer first pregnancies compromised by Pregnancy-Induced-Hypertension (PIH) than did women in the control group (T1+T2).⁶³ While this difference was only statistically significant when T3 and T4 were contrasted with T1 + T2, the pattern held for the two groups followed after delivery, T2 and T4. Nurse-visited women overall had lower rates of preterm birth, and those with low psychological resources (LPR) measured at registration had fewer low birth weight newborns than did their control-group counterparts.⁷² This reduction was significant when the contrast was limited to the two groups followed after delivery (T2 vs T4). Note also differences in self-reported prenatal health behaviors at 36 weeks of gestation for mothers of females.

Short Inter-Pregnancy Intervals. Nurse-visited women (T4) had greater intervals between their first and second births,⁶³⁻⁶⁵ and had fewer closely spaced subsequent births over the 12-year period following birth of the first child,⁶⁸ an important contributor to maternal health.⁷⁶

Table 3. Program effects on selected maternal outcomes through age 18

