relationships, family economic resources, and hypertension at 12 and 18 years postpartum. H9: NV effects on offspring outcomes (H1-6) will be mediated, in part, by NV effects on prenatal health behaviors, preterm delivery, PIH, breast feeding, screen time at age 12, improved partner relationships, family economic resources through age 18, and obesity and prehypertension at ages 12 and 18. Tests of mediation will follow the empirical and theoretical model shown in Figures 1 and 2. We will employ mediation analyses using structural equation models to examine causal processes, including the direct and indirect effects of treatment on outcomes.^{100,101} To illustrate, we have hypothesized that NV will have an indirect effect on maternal arterial stiffness through its effect on PIH, preterm delivery, and the count of short inter-pregnancy intervals. To test one aspect of this hypothesis, we will regress maternal arterial stiffness on the count of closely spaced subsequent children (child density) within the control group; we also will regress child density on the treatment contrast. If the paths from the control sample to child density and from density to arterial stiffness are both significant, we will have met the joint significance test criterion. We will next calculate the indirect effect, based on these same two path coefficients, and compare the resultant z' to Mackinnon's table of critical values. If the z' is equal to or higher than the appropriate critical value, we will conclude that density of subsequent children mediates the effect of nurse visitation on maternal arterial stiffness. We will use this approach for each hypothesized mediator separately and jointly to develop a map of mediation.

Challenges in the Conduct of This Work

Missing Data. Missing data in this trial have been remarkably low. We are sensitive to the potential pitfalls of analyzing only cases with complete data.¹⁰⁵ We have complete data on all relevant background characteristics, which we will examine to address potential attrition bias. We also will compare our analyses to the same analyses employing inverse proportional weighting. We will perform sensitivity analyses to ensure that results are similar under various assumptions. We will determine whether imputation is valid and has sufficient added value with our data to justify the complexity involved in reporting these analyses.

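### H8 and H9 extend mediation to mortality through postnatal mediators that some deaths precede or cut short, with no landmark, arm restriction or survival-mediation model

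*Combined protocol and SAP*

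**What the plan says.** Under Tests of Hypotheses, H8 reads "NV effects on maternal outcomes (H1-6) will be mediated, in part, by NV effects on prenatal health behaviors" and H9 reads "NV effects on offspring outcomes (H1-6) will be mediated, in part, by NV effects on prenatal health behaviors, preterm delivery, PIH, breast feeding". The Approach to Specific Aim Three repeats the H1-6 scope for H9. H7, in the same section, is limited to H1-5 and exempts mortality because of low base rates. H8 and H9 carry no such exemption.

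The late mediators include, for mothers, "relationships, family economic resources, and hypertension at 12 and 18 years postpartum" and, for offspring, "family economic resources through age 18, and obesity and prehypertension at ages 12 and 18", together with screen time at age 12. H8 also lists closely spaced subsequent pregnancies and preterm delivery in first and subsequent births.

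One method is given: structural equation models, a joint-significance test, and a product-of-coefficients statistic compared with tabulated critical values. It is illustrated with arterial stiffness and is to be used for each hypothesized mediator, separately and jointly. H6 itself is a survival analysis.

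On arms, Section I says "we will assess maternal and offspring mortality in all four of those treatment conditions". Under Treatment Conditions, T1 had no postpartum assessments except maternal death records. For T3 the text is "This group did not receive any other postpartum services or assessments (except death records".

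**The concern.** A mediator has to come before the outcome it explains. A person who died before the year-12 or year-18 visit has no value for a measure taken then. A complete-case analysis of that measure drops those deaths, and they are part of the mortality difference to be explained.

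A cumulative mediator fails in another way. Counts of closely spaced births, or summed benefit payments, stop at death. Early death then looks like few births or low benefits, which creates an inverse association with no causal content. H8 expects fewer closely spaced births to go with lower mortality, so this artefact works against finding the pathway.

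The Missing Data section offers weighting, sensitivity analyses and possibly imputation. None of these addresses a value that is undefined because the person has died.

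**Working it through.** **1. Table 2 reproduces.** Mothers available: 742 − 27 − 7 − 8 − 18 − 25 = 657. Offspring available: 742 − 27 − 7 − 8 − 11 − 2 = 687. Both match, so the death counts can be used.

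**2. Deaths set against the timing of the mediators (T2 and T4).**
- Mothers: the row "Maternal deaths through 18 years postpartum" gives 15 + 3 = 18, that is 15/514 = 2.9% in T2 and 3/228 = 1.3% in T4. All 18 precede or preclude the year-18 measure. The number before year 12 is not given.
- Offspring: 8 deaths before age two (7 + 1) and 11 after (9 + 2), 19 in all. The first 8 (8/19 = 42%) precede any age-12 or age-18 measure. The ages of the other 11 are not given, so 8 is a floor.

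**3. Arms without postnatal mediators.** T1 + T3 = 166 + 230 = 396, and 396/1,138 = 34.8%.

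**4. Mediators that keep the right order.** Per the Table 3 notes, PIH and preterm delivery come from the labor, delivery and newborn record. The health-behavior index comes from the 36-week interview. PIH is reported for T1+T2 versus T3+T4 and for women who died in T3 and T4. It is the only mediator for which four-arm data are shown explicitly. Preterm delivery in subsequent births is postnatal.

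**5. Illustrative size of the truncation artefact.** Assumptions: closely spaced births follow a Poisson process with mean 0.51 over 12 years (control value, Table 3) and stop at death; 3.7% are dead at 21 years (T1+T2, Table 3); births have no effect on death. Survival is S(t) = 0.963^((t/21)^k), with k = 1 for a constant hazard and k = 2 or 3 for a rising one. Death by the horizon is regressed (logistic) on the final birth count. Follow-up through 2026 is about 2026 − 1990 = 36 years after registration.

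| Hazard | Dead at 36 y, 1 − S(36) | OR per birth, 21 y | OR per birth, 36 y |
|---|---|---|---|
| k = 1 | 6.3% | 0.71 | 0.83 |
| k = 2 | 10.5% | 0.89 | 0.96 |
| k = 3 | 17.3% | 0.95 | 0.99 |

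The true value is 1.00 throughout. Restricting to women alive at year 12 and counting only later deaths returns 1.00 in every row. With 514 control women, the 36-year bias is about 0.7 standard errors for k = 1 and 0.2 for k = 2.

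**6. Events left after a year-18 landmark.** Total T2+T4 maternal mortality through 2026 is not given. Assuming 4%, 6%, 8%, 10% or 12% of 742, total deaths are 30, 45, 59, 74 or 89. Subtracting 18 leaves 12, 27, 41, 56 or 71. Power for an assumed hazard ratio of 0.5 (Schoenfeld, allocation 228/742) is then 20%, 38%, 54%, 67% or 77%. That is for the treatment effect alone, before any mediation test.

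**The case against.** The strongest reply is that this is loose wording in an exploratory aim. Aim 3 speaks of exploring mediators on selected outcomes, and the protocol calls its pathway models complex. The general methods list includes Cox and competing-risks models. This lowers the priority but does not remove the point: the operative text names H1-6 and gives one rule that ends in a stated conclusion about mediation.

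A reader might infer that mediation of mortality is invalid altogether. The documents do not support that. First-birth prenatal and delivery mediators precede the long-term deaths, and PIH exists in all four arms. Mastery, partnership, births and benefits were also recorded from early waves, so many women who died will have earlier values. The plan does not say which values would be used.

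A reader might also infer that the sponsor plans four-arm mediation with data that do not exist. Mortality is assessed in four arms, but the mediation text names none. This part is under-specification.

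Nor can one state what share of all deaths lacks a year-18 value. Table 3 implies 680 × 3.7% + 458 × 1.3% ≈ 25 + 6 = 31 deaths at 21 years, from rounded rates and well short of 2026. Those counts also sit badly with the Figure 1 discussion: PIH in 14% of T4 deaths needs at least 7 deaths and 25% of T3 deaths at least 4, so 11 or more against about 6. These figures need reconciling first.

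Finally, the artefact is inverse and the rule requires both paths to be significant, so it would mask mediation more readily than create a false claim. The plan also does not state a logistic model for H6.

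**Conclusion.** The point stands for postnatal mediators of mortality. Hypertension at 12 and 18, screen time at 12, and obesity or prehypertension at 12 and 18 cannot mediate deaths that came before them. Closely spaced births and benefits are cut short by death. T1 and T3 lack postnatal study assessments. The plan has no rule for any of this, so the stated analysis is not valid for these mediators.

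The counts in steps 2 and 3 come directly from the documents. The odds ratios rest on the assumptions in step 5 and show direction and range only. At the 2026 horizon the artefact is small to modest, and it is smaller if mortality rises with age, as Section I expects for natural causes. The loss of early deaths from year-12 and year-18 analyses does not depend on those assumptions. Because the aim is exploratory, the priority is moderate.

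**What to change.** In H8 and H9, limit mediation of H6 to mediators fixed by the first delivery: prenatal health behaviors, PIH and first-birth preterm delivery. Use all four arms where the mediator was measured in all four, and say which those are.

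For every postnatal mediator, including preterm delivery in subsequent births, choose one of two courses:
- write H1-5, so that mortality is out of scope; or
- use T2 versus T4 only, in a time-to-event mediation model with a landmark at the mediator visit that counts only later deaths (or with births entered as time-varying). State that the result does not explain deaths before the landmark.

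The change is to analysis-plan wording; no new data are needed. The cost is fewer deaths and less precision in the landmark analyses, on the scale shown in step 6. Mortality follow-up runs through 2026, so the rule can be fixed before the final mortality data are in.
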